11.1. Criteria for inclusion of subjects

- Over 18 years of age.
- Autonomy, self-sufficiency and independence.
- Indication of CL programmed:
 - Symptomatic cholelithiasis: history of biliary colic, acute calculous cholecystitis, choledocholithiasis, acute ascending cholangitis of calculous origin or acute calculous pancreatitis.
 - Gallbladder polyps with indication for laparoscopic surgery.
 - Vesicular adenomyomatosis with indication for laparoscopic surgery.
- Indication for early LC (<72 hours of admission for acute calculous cholecystitis/acute calculous cholecystitis/complicated biliary colic).
- Indication of deferred emergency CL.
- Understanding information.
- Signing the informed consent form.

11.2. Exclusion criteria for subjects.

- Under 18 years of age.
- Incapacity.
- Pregnancy or breastfeeding.

- Chronic kidney disease (Stage> IIIb).
- Adverse reactions or allergies prior to IV.
- Previous adverse reactions or allergies to VI excipients.
- Confirmed adverse reactions or allergies to iodinated contrast agents.
- Functional thyroid pathology (hyperthyroidism, thyroiditis, toxic multinodular goitre, functioning thyroid adenoma).
- Urgent non-deferrable/emergent gallbladder surgery.
- Initial surgery by laparotomy.
- Previous suspicion of gallbladder carcinoma.
- Inability to understand the information needed to participate in the study.
- Refusal of inclusion in the study protocol.

11.3. Termination and interruption criteria

- **Study termination criteria.** Completion of the 30-day follow-up period of the last patient included in the study.
- **Patient completion criteria.** Completion of the follow-up 30 days after the intervention.
- **Patient discontinuation criteria.** At least one of the following must be met:
 - Serious adverse events related to drug administration.
 - Development of contraindications or study exclusion criteria within the inclusion period and prior to surgery.
 - Voluntary drop-out of previously included patients.

12. Informed Consent (IC) and Patient Information Sheet (PIS)

The investigator will explain to each patient (witness or legal representative) the nature of the study/trial and the purposes, procedures, estimated duration, possible risks and benefits of their participation in the study/trial and possible inconveniences that this may cause them. All patients will be informed of the voluntary nature of their participation and that they may withdraw at any time, without affecting their future medical care or their relationship with the physician responsible for their treatment.

The patient shall be given sufficient time to read and understand the explanations included in the patient information sheet before giving informed consent (Annex 3). No patient shall be included in the study/trial before informed consent has been obtained.

Each patient will be assigned to an intervention group which will involve the administration of a dose at a predetermined time. All patients will receive the study product as there is no placebo group. The reason for the existence of 4 comparative groups is to study the efficacy of different dosage and interval of administration of the IV. Participation in the study

does not involve a different surgical procedure or an increase in the number of scheduled visits.

13. Data Collection Notebook -CRD-

The data collected will be recorded in a CRD, the veracity of which will be validated by the designated monitors. Each patient will be identified in the CRD by means of an alphanumeric code that identifies the patient (and the centre if it is a Multicentre) and in correlative order. The data protection provisions of Organic Law 3/2018 on Personal Data Protection and guarantee of digital rights will be respected at all times.

The data will be obtained from the personal interview with the patient and access to the patient's clinical history. If the patient does not attend any of the scheduled visits, the investigator will contact the patient by telephone to confirm that the absence is not due to a conscious abandonment of follow-up. If the patient is not contacted, the researcher will access the local or regional digital medical record to find out if there have been any events related to the study that have been assessed in another health centre.

The procedures for correctly completing the data collection notebook will be through the specific sessions of the General and Digestive System Surgery Department, by means of the presentation and explanation of the notebook. In addition, any doubts and problems that may arise will be resolved.

The specific requirements will be determined by the electronic data collection record keeper:

1. The principal investigators (PIs) will be the only individuals who can sign the registry. These individuals have all functions with the exception of the monitor function and the electronic data collection logbook manager (CRDe).

2. Sub-researchers and study coordinators may include data in the study, but may not sign the registry. You can resolve *queries*.

3. The monitor will be able to review the data and generate *queries*.

4. The data manager has the power to block-unblock the electronic data collection logbook. In addition, he/she is responsible for data management. He/she has access to all the centres included in the study.

Randomisation will be carried out using algorithms proposed by the CRD. Block randomisation will be carried out.

All patient data will be included for the first 45 days after the patient's surgery.

14. Medical History -HC- and source documents

The electronic medical record will be available through the Jimena computer software (version III and version IV) of the Castilla y León Health System (SACYL) and the SAP software of the Catalan Health System. In addition, those paper documents that must be kept in the medical record and cannot be computerised (informed consent for surgery, informed consent for clinical trials, surgical protocol, hospital discharge report), will be collected in the paper medical record of each patient, and stored in the Clinical Documentation Service of the University Hospital of Salamanca and the University Hospital of Salamanca.

Germans Trias i Pujol University of Badalona. Paper documents can be scanned and stored in the digital repository of both servers.

Definitions:

- Source data: All information in original documents and certified true copies of original records of clinical results, observations, or other activities of a clinical trial necessary for the reconstruction and evaluation of the trial. Source data shall be included in the source documents (original records or certified copies).
- Source documents: original documents, data and records (e.g., patient records, medical or consultation records, laboratory notes, memoranda, registers, data recorded on automated instruments, copies or transcripts certified after verification, microfiche, photographic negatives, microfilm or magnetic media, X-rays, subject files, and pharmacy records in the laboratories and in the medico-technical departments involved in the clinical trial).

Patients must have given written consent for their medical records to be read by personnel authorised by the sponsor and regulatory authorities. This information is included in the informed consent.

The following data specific to this CB shall be collected in the HC and shall also be collected in the CRDe:

- **Pre-operative period:**
 - Date of birth (dd-mm-yyyy), age (years), sex (male/female), weight (kg), height (cm), body mass index-BMI (kg/m²), anaesthetic-surgical risk classification (American Association of Anaesthesiologists-ASA classification), previous abdominal surgeries (biliary tract, liver, pancreas, intestinal, others), previous endoscopic or radiological explorations of the biliary tract (endoscopic retrograde cholangiopancreatography (ERCP) or endoscopic retrograde cholangiopancreatography (ERCP)), liver, pancreas, intestinal, others), previous endoscopic or radiological explorations of the biliary tract (endoscopic retrograde cholangiopancreatography (ERCP) or transparihepatic cholangiography (TPHC)), previous biliary prosthesis placements (yes/no). History of acute cholecystitis (yes/no). /previous acute cholangitis (yes/no). History of previous percutaneous gallbladder drainage (no/radiological percutaneous cholecystectomy or endoscopic transduodenal/transgastric). Previous liver disease (no/fatty liver steatosis/hepatitis/cirrhosis).
 - Indication for surgery [Symptomatic cholelithiasis (biliary colic, acute cholecystitis, choledocholithiasis, acute ascending cholangitis, acute lithiasic pancreatitis), gallbladder polyps, gallbladder adenomyomatosis].
- **Perioperative period:**
 - Date of entry (dd-mm-yyyy).
 - Time of entry (hour:minutes)
 - Date of surgery (dd-mm-yyyy).
 - Time of surgery (hour:minutes).

- Type of surgery (elective/early/ delayed emergency).
 - Grade of cholecystitis in case of early surgery / delayed emergency (18th Tokyo Classification).
 - Intervention group (group 1/group 2/group 3/group 4).
 - Characteristics of the procedure. IV dosage (fixed dose/weight-adjusted dose). IV administration interval (>3 hours preoperatively, 15-30 minutes preoperatively). Immediate adverse reactions (yes/no. Specify). Number of trocars (3/4). Imaging system used (Olympus/Karl-Storz/Stryker). Optics used (0º/30º). Gall bladder puncture/emptying (yes/no). Bile culture (yes/no). Result of bile culture if any (specify).
 - Conversion to laparotomy (yes/no), intraoperative complications (yes/no), specification of intraoperative complications (cystic artery injury, right hepatic artery injury, liver injury with/without bleeding, gallbladder opening (intrapertitoneal biliary contamination: yes/no, lithiasis outflow into peritoneal cavity: yes/no), hollow viscus perforation, trocar bleeding, other). Operating time (minutes).
- **Postoperative period:**
 - Hospital stay (days), postoperative complications (intra-abdominal haematoma, bilioma, abscess, paralytic ileus, surgical site infection-ISQ, trocar evisceration, trocar eventration, others), postoperative complications according to Clavien-Dindo classification, bile duct injury (Strasberg classification), time of diagnosis bile duct injury (intraoperative / postoperative), treatment of bile duct injury (immediate surgical, radiological, endoscopic or delayed surgical). Mortality during admission (yes/no), 30-day mortality (yes/no), causes of mortality (specify). Adverse drug reactions within 30 days (yes/no. Specify).

All preoperative data will be collected for patients withdrawn from the study, as well the type of complication developed and any adverse events during the first 30 days of the study (if any). Subjects will not be replaced in the study. The follow-up period will be identical for subjects who do not undergo the study intervention.

15. Monitoring

Required data to be accurately recorded in CRDs and agree with source data. Revised according to the Monitoring Manual.

- Patient identification.
- Date and time of surgery.
- Dose and time of VI administration.
- Target variables (set out above).

After each monitoring, the monitor will be able to generate a discrepancy document with the inconsistencies and errors detected in the study. These problems can be communicated through the CDRe or by e-mail.

16. Researcher and collaborators

The principal investigator shall maintain a register of all persons involved in the trial (medical, nursing, and other personnel). He/she shall confirm that appropriate training relevant to the trial is given to all such personnel and that any new information relevant to the conduct of the trial is conveyed to the personnel involved.

17. Facilities

- **Hospitalisation ward.** This is where the patient is admitted prior to surgery. This is where all mandatory documentation is checked and the patient is prepared for surgery.
- **Pre-operative conditioning room.** A surgical checklist and a new preparation of the patient will be performed.
- **Operating theatres.** In addition to the equipment necessary for any laparoscopic surgical activity, which is no different from the study activity, these operating theatres will be equipped with the necessary equipment to perform CF-VI (optics, light cable and compatible image processing system).
- **Postoperative recovery room.** Controlled by the Anaesthesiology and Resuscitation Service.
- **Outpatient clinics.** Place where the postoperative control will be carried out after the patient is discharged.
- **Hospital Pharmacy Service.** Responsible for dispensing the medicine.
- **Operating theatre storeroom.** This is where the necessary equipment and drugs are stored, including the active ingredient of the study.

[figure not shown]
18. Treatment of Subjects

Subjects included in this CE will be treated with VI [Verdye (Diagnostic Green GMBH, Aschheim-Dornach, Germany)]. The following patient groups are established in the CE.

- **Group 1.** Fixed dose 2.5 mg with IV administration more than 3 hours before surgery.
- **Group 2.** Fixed dose 2.5 mg with immediate pre-operative VI administration (15-30 minutes before surgery).
- **Group 3.** Weight-adjusted dose (0.05 mg/kg total body weight) with administration of the LV more than 3 hours before surgery.
- **Group 4.** Weight-adjusted dose (0.05 mg/kg total body weight) with immediate pre-operative administration of the IV (15-30 minutes prior to surgery).

Verdye contains the active substance VI sodium powder for solution for injection. Each ampoule contains 25 mg of active substance. The dissolution medium for the product should be water for injectable preparations. The solution for injection should be inspected before administration and discarded in case of turbidity. The drug solution shall be prepared with 10 ml of water for injectable solutions, obtaining a ratio of 2,5 mg/ml. Once the solution is prepared according to the above protocol, it shall be injected directly through a peripheral venous line of the patient's upper limb. The medicinal product should be stored at a temperature below 30°C, keeping its original outer packaging in order to protect the medicinal product from light. Once the solution for injection has been prepared, it should be protected from light and used immediately.

The expected duration of subject participation will be 31 days, including preoperative, intraoperative, immediate postoperative (<24 hours), early postoperative (<7 days) and late postoperative (<30 days) periods. The patient recruitment period will be 12 months. The end of the clinical trial will take place from day 30 after discharge of the last patient recruited, with the aim of analysing the 30-day morbidity and mortality of the study patients.

* El periodo de lista de espera quirúrgica podría variar entre pacientes según necesidades asistenciales.

** El periodo postoperatorio normal tras colecistectomía laparoscópica programada es de 24-48 horas. No obstante, puede ampliarse debido a complicaciones y/o necesidades.

The frequency of patient visits will be as follows:

- 1- **Consultation prior to admission.** The objective of the study and the entire study protocol will be explained, along with the delivery of the HIP and the IC.
- 2- **Visit prior to surgery.** This visit will corroborate the correct understanding of the information, the presence of the correctly signed ICs and the resolution of any doubts or problems.

- 3- **In-hospital post-operative visits.** These will be carried out daily in the morning shift (8-15 hours). No different from postoperative visits of other operated patients.
- 4- **Postoperative control visit.** This will take place 30 days after the surgical intervention through the General and Digestive System Surgery Outpatient Department.

There is no treatment period as it is considered a diagnostic method. This period shall include intraoperative time.

A computerised block randomisation will be performed through CDRe. Participants will be assigned to each of the 4 treatment groups by non-stratified 1:1:1:1 randomisation.

As it is an intervention without a control group, blinding will not be performed in the trial. The end-of-study criterion will be completion of the follow-up period at the end of the trial. 30 days from the last patient included in the study.

19. Effectiveness Assessment

The following efficacy parameters shall be used:

- Degree identification of biliary structures prior to dissection of the hepatocystic triangle (1=poor, 2=sufficient, 3=sufficient, 4=good, 5=excellent).
- Degree of identification of biliary structures after dissection of the hepatocystic triangle (1=poor, 2=sufficient, 3=sufficient, 4=good, 5=excellent).
- Degree to which FC was perceived as useful for surgery (0=not useful, 1=moderately useful, 2=very useful).
- Degree to which the fluorescence of the liver background (contrast between liver and ducts) was perceived as disturbed (0=absence of disturbance, 1=slightly disturbed, 2=disturbed visualisation, but cystic-choledochal junction was clearly visible before dissection, 3=disturbed visualisation and cystic-choledochal junction was only visible after dissection, 4=very disturbed: it was impossible to visualise the biliary structures correctly).

20. Security Assessment

20.1. Definitions

- **Adverse Event (AE):** An adverse event is any undesirable medical reaction experienced by the patient at any time during the course of the study, whether or not it is considered to be related to the study treatment. This definition includes new disease onset and exacerbation of pre-existing conditions other than the indication under study.
- **Adverse Reaction (AR):** An AR is any unintended, harmful reaction to an investigational medicinal product, regardless of the dose administered.

- **Serious Adverse Event (SAE) and Serious Adverse Reaction (SAR)**

Serious AEs or ARs are considered to be those which, at any dose, may result in **death, threaten the life of the subject, require hospitalisation of the patient or prolong an existing hospitalisation, cause permanent or major disability or incapacity, or result in a congenital anomaly or malformation. Suspected AE or AR that is medically significant**, even if it does not meet the above criteria, including major medical events that require intervention to prevent one of the consequences described above, **are also considered serious**. In addition, all suspected transmission of an infectious agent via a medicinal product shall be reported as serious.

The concept of "threatening the life of the subject" in the definition refers to the fact that, in the opinion of the investigator, the patient at the time of the AA or AR is at real risk of death; it does not refer to the fact that the AA/AR hypothetically could have resulted in death had it been more severe.

The term "requiring hospitalisation" shall exclude both planned hospitalisations for scheduled treatments and hospitalisations that have been planned or are anticipated prior to the start of the study in relation to a pre-existing medical condition.

- **Unexpected Adverse Reaction (UAR)**

Any AR whose nature, intensity or consequences do not correspond to the reference safety information.

- **Serious Unexpected Adverse Reaction (SUAR)**

RAG (previously defined), the nature, severity or consequences of which do not correspond to the reference safety information.

20.2. Causality Criteria (see section 20.7)

- **Related AA:** The temporal relationship of the AA with the study medication indicates a possible causal relationship and cannot be explained by factors such as the patient's clinical status, therapeutic interventions.

- **Unrelated AA:** The temporal relationship of the AA to the study medication indicates an unlikely causal relationship, or other factors (medication or concomitant conditions), other therapeutic interventions provide a satisfactory explanation for the AA.

20.3. Security reference information

In this study, the reference safety information (RSI) will be the information available in the corresponding product label of the medicinal product under study: Verdye.

20.4. Safety variables and parameters

The safety assessment of the drugs under study will be carried out by means of clinical examination (physical, analytical and/or radiological) and collecting serious adverse effects and those that may be directly related to the medication under study.

The key safety parameter will be the bile duct injury rate, which is currently at incidences of 0.3%-0.7%.

20.5. Information on Adverse Events

All adverse events shall be recorded in the data collection notebook. For each adverse event, the dates of onset and resolution, intensity, duration, and its impact on study treatment (e.g. discontinuation) shall be recorded. The severity of the adverse event and its relationship to the study should be assessed according to specific guidelines. Any action taken or outcome achieved (e.g. hospitalisation, withdrawal of treatment, etc.) should also be noted.

The investigator or a co-worker shall question and/or examine the subject for the occurrence of adverse events.

Adverse events will be collected once the subject has been randomised. If a subject experiences an adverse event after signing the informed consent document (inclusion), but prior to treatment assignment (recruitment), the event will NOT be recorded unless the investigator considers it to be causally related to a procedure in the protocol.

During the course of the study, site staff will again note any changes in the disorder and nature of possible adverse events.

20.6. Assessment of the intensity of adverse events and their relation to treatment

The following definitions shall be used to assess the intensity of adverse events:

- Mild: sign, symptom or event is known but easily tolerated.
- Moderate: there is sufficient discomfort to interfere with normal activity and may warrant intervention.

- Severe: is disabling and results in inability to perform usual activities or significantly affects the clinical condition and warrants intervention.
- Life-threatening: immediate risk of death.
- Death

20.7. Assessment of the imputability of adverse events and serious adverse events with study treatment: Imputability criteria.

The sponsor will classify adverse events, based on their causal relationship with the drug, according to the Algorithm of Karch and Lasagna (1977), as follows:

- **Definitive:** there is a reasonable time sequence between the administration of the drug and the appearance of the AE. The event coincides with the ARs described for the drug, improves with drug withdrawal, reappears after re-administration and cannot be explained by alternative causes.
- **Probable:** there is a reasonable time sequence between the administration of the drug and the occurrence of the AE. The event coincides with the ARs described for the drug, improves after discontinuation of treatment and cannot be explained by other alternatives.
- **Possible:** there is a reasonable time sequence between drug administration and the occurrence of AA. The event coincides with the ARs described for the drug but can be explained by alternative causes.
- **Conditional or Improbable:** there is a reasonable time sequence between the administration of the drug and the occurrence of the AE. The event does not coincide with the ARs described for the drug and can be explained by alternative causes.
- **Unrelated:** there is no reasonable time sequence between the administration of the drug and the occurrence of the AE. The event does not coincide with the ARs described for the drug and can be explained by alternative causes.

For the purposes of expedited reporting, the definite, probable and possible categories of the Karch and Lasagna (1977) algorithm shall be considered as related and the conditional or improbable category of the Karch and Lasagna (1977) algorithm shall be considered as unrelated.

The determination of the possible relationship to the study treatment is the responsibility of the principal investigator of the research site or his/her designee and, once notified, will be reviewed by the study sponsor and/or his/her designee.

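### Protocol Sections 20.2 and 20.7 give conflicting causality rules, and the 20.7 rule leaves a reaction new in nature no route to being classed as related for expedited reporting

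*Protocol*

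**What the plan says.** Section 20.2 of the protocol, whose heading refers the reader to 20.7, has two classes. An event is related if its timing suggests a possible causal link and it "cannot be explained by factors such as the patient's clinical status, therapeutic interventions". It is unrelated if the timing makes a link unlikely, or if "other factors (medication or concomitant conditions), other therapeutic interventions provide a satisfactory explanation for the AA". Whether the reaction is already known plays no part.

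Section 20.7 adopts a named published algorithm with five categories. For well-timed events the conditions are:

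- *Definitive*: "The event coincides with the ARs described for the drug, improves with drug withdrawal, reappears after re-administration and cannot be explained by alternative causes".
- *Probable*: "The event coincides with the ARs described for the drug, improves after discontinuation of treatment and cannot be explained by other alternatives".
- *Possible*: "The event coincides with the ARs described for the drug but can be explained by alternative causes".
- *Conditional or improbable*: "The event does not coincide with the ARs described for the drug and can be explained by alternative causes".

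The fifth category, *Unrelated*, repeats that last sentence for events without reasonable timing. For expedited reporting, the first three categories count as related and *Conditional or improbable* counts as unrelated.

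Section 20.1 defines an unexpected reaction as "Any AR whose nature, intensity or consequences do not correspond to the reference safety information", and defines the serious unexpected reaction in the same way. Section 20.3 sets the product label as the reference safety information. Section 20.9 requires all serious unexpected reactions to be notified to the authorities within 15 calendar days, or 7 where the patient died or was endangered.

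**The concern.** Expedited notification applies to an event that is serious, unexpected and related. The protocol defines unexpectedness separately, against the label. Section 20.7 nevertheless builds a form of it into causality, because an event must resemble a described reaction before it can count as related. A reaction of a kind not yet described, which is one of the things expedited reporting exists to catch, then fails the causality test for the same reason that it is unexpected.

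Section 20.2 does not share this condition, so two assessors who follow different sections can classify the same event differently. The sections also part company, in the other direction, over a known reaction that has another explanation. At stake is whether a serious reaction new in nature is notified individually and on time, and whether relatedness is recorded consistently across sites.

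**Working it through.** The plan gives no figure on this point, so there is none to reproduce. The check applies both rules as written to every combination of three yes/no features: reasonable timing, match with described reactions, and an alternative cause. Improvement on withdrawal and reappearance on re-administration were varied within each combination. Alternative cause is taken here to mean one good enough to meet both sections' wording.

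| Timing fits | Described | Alternative cause | Section 20.2 | Section 20.7 and its class for expedited reporting |
|---|---|---|---|---|
| yes | yes | yes | unrelated | *Possible*: related |
| yes | yes | no | related | *Definitive* or *Probable*: related; no category if improvement on withdrawal is not shown |
| yes | no | yes | unrelated | *Conditional or improbable*: unrelated |
| yes | no | no | related | no category |
| no | yes | yes | unrelated | no category |
| no | yes | no | unrelated | no category |
| no | no | yes | unrelated | *Unrelated* (not named in the mapping) |
| no | no | no | unrelated | no category |

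Three results follow.

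1. **Row 1 is a direct contradiction.** A described, well-timed event with a satisfactory alternative explanation is unrelated in 20.2 and related in 20.7.
2. **Row 4 is a gap.** An undescribed, well-timed event with no other cause is related in 20.2. In 20.7 it fails the first three categories because it is not described, and fails *Conditional or improbable* because it has no alternative cause.
3. **Undescribed events never reach related under 20.7.** There are 2 × 2 = 4 combinations of timing and alternative cause for such events (rows 3, 4, 7 and 8), and 0 of 4 reach it, whatever happens on withdrawal or re-administration.

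Row 2 shows a smaller gap of the same kind. Section 7 describes a bolus and Section 18 says there is no treatment period, so improvement after discontinuation may be hard to establish. A described event with no other cause can then also be left without a category.

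**The case against.** The strongest reply is that such events do not disappear. Section 20.9 sends every serious adverse event to pharmacovigilance within 24 hours, regardless of causality or expectedness. It also requires information that could change the risk/benefit balance to be reported within 15 days. Section 20.11 puts the collected serious events in the annual safety report. All of this stands. A reader might infer that the safety signal is switched off, and the documents do not support that. These provisions do not correct the classification, however, and the individual expedited notice depends on it.

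Four other stronger readings also fail:

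- **That every unexpected reaction is blocked.** Section 20.1 also counts reactions unexpected in intensity or consequences. These can match a described reaction and so be classed as related.
- **That every *Possible* event changes class between sections.** *Possible* needs only that another explanation can be offered, whereas 20.2 needs a satisfactory one. Events with a satisfactory explanation conflict; the rest are not shown to.
- **That the protocol leaves open who decides.** Section 20.7 opens by saying that the sponsor classifies, but it closes with "The determination of the possible relationship to the study treatment is the responsibility of the principal investigator" (or a designee), followed by sponsor review. The opening wording is loose, no more.
- **That deleting the described-reaction condition is enough.** Without it, *Possible* would cover any well-timed event with an alternative cause. It would then overlap *Conditional or improbable*, with one counted as related and the other as unrelated.

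**Conclusion.** The concern holds in this form. Sections 20.2 and 20.7 conflict on a described, well-timed event with a satisfactory alternative explanation, and on an undescribed, well-timed event with none. Under 20.7 a reaction new in nature cannot be classed as related (0 of 4 combinations). It can therefore miss the individual expedited notification that Section 20.9 requires for all serious unexpected reactions.

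The risk is confined to that route. The documents give no basis for estimating how many events would be affected.

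Two assumptions matter. First, the protocol does not define which described reactions it means. If the set is wider than the label, a reaction described elsewhere but absent from the label could be both related and unexpected; a wholly new one still could not. Second, the row 1 conflict needs an alternative explanation that meets both sections' wording. The point should be corrected, but it does not bear on the trial's design or efficacy analysis.

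**What to change.** Reconcile Sections 20.2 and 20.7 into a single scheme and state that it is the one used for expedited reporting. Within it:

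- Assign the uncovered combination (reasonable timing, not described, no alternative cause) to a category that counts as related. Expectedness is then judged only against the reference safety information and is not a precondition for causality.
- State which rule governs when an alternative explanation exists, and how good that explanation must be, keeping *Possible* and *Conditional or improbable* distinct.
- Say how the *Unrelated* category maps, and where a described event goes if improvement on withdrawal cannot be shown.
- Say whether the reworded scheme is still the named algorithm or an adaptation of it.
- Align the opening of 20.7 with its closing paragraph on who determines causality and who reviews it.

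The cost is rewording of two sections. Some more events may need expedited review; the documents do not allow the number to be estimated. No visit, sample size or analysis changes.
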